5.6 Dose Escalation Criteria (DEP)

In the absence of >33% of patients experiencing a drug-related DLT, escalation to the next dose level for a given treatment arm may proceed when all of the following have occurred:

- At the completion of Cycle 1 (treatment cycle = 28 days for DR-A and DR-A-2 or treatment cycle = 21 days for DR-B),
- The Safety Review Meeting is convened during which the Safety Review Committee (SRC), consisting of the Investigators and Sponsor's Medical Monitor, has reviewed all available safety data for all patients in the cohort and confirms that the next planned dose level is appropriate; and
- The Sponsor Medical Monitor issues written documentation of the decision to proceed to the next planned dose level of a dose regimen.

It is important to note that despite the absence of >33% of patients experiencing a DLT, the next dose level may be less than the planned dose level if the Investigators and Sponsor's Medical Monitor agree that a more conservative dose escalation approach is warranted or would be in the best interest of the patients. The SRC may hold the dose (e.g., stop dose escalation) at their discretion and enroll additional patients until sufficient safety data are obtained to determine escalation of the current dose level or to confirm a certain dose as an MTD or OBD.

5.7 Planned Dose Levels

[figure not shown]
5.7.1 Dose Levels for the Dose Escalation Portion of the Study

In the Dose Escalation portion of the study, increasing dose levels of ALRN-6924 will be evaluated in cohorts of 3-6 DLT-evaluable patients per dose regimen. Patients enrolled in Cohort 1 receive ALRN-6924 at Dose Level 1 (0.16 mg/kg). Based on allometric scaling, at 0.16 mg/kg dose in humans, the predicted AUC (50 $\mu\text{g}\cdot\text{hr}/\text{mL}$) is approximately 9% of the rat AUC at STD_{10} and approximately 6% of the AUC at the monkey HNSTD as described in Section 1.4.

In the absence of DLT in >33% of DLT-evaluable patients in either DR, subsequent cohorts of 3 to 6 patients will receive escalated doses until the MTD or an OBD is established for each dose regimen.

A 2-stage dose escalation design will be employed. During the initial Stage 1 Escalation Phase, 100% dose increments will be utilized until ≥ 1 of 3 patients in a cohort experiences any Grade ≥ 2 AE that is at least possibly related to study drug. Study drug-related AEs Grade ≥ 2 occurred in DL-4A (fatigue) and in DL-3B (neutropenia). Therefore, per protocol, Stage 2 has been implemented for subsequent dose escalations starting with DL-5A and DL-4B. Dose escalation will continue using 3-patient cohorts and the modified Fibonacci sequence (i.e., 67%, 50%, 40%, 33%), until the MTD or an OBD is established. As two DLTs have occurred in DR-7A (hypotension and hepatobiliary laboratory abnormalities), there will be no further dose escalation in DR-A. A new modified infusion regimen was tested (DR-A-2) starting at dose level 7A-2 (=4.4 mg/kg body-weight). As two DLTs have occurred in DR-7A-2 (anemia and neutropenia), there will be no further escalation in DR-A-2.

Figure 9: Dose Level and Dose Regimen Schematic

The observation of DLT(s) will be used to make individual patient determinations regarding dose reductions, interruptions or discontinuation throughout the course of the trial, but DLTs occurring during Cycle 1 will be used to inform safety and tolerability assessments for dose escalation decisions.

If DLTs are observed in the first cohort, the dose will be de-escalated to Dose Level -1. If DLTs are observed at Dose Level -1, the dose will be de-escalated to Dose Level -2. If DLTs are observed at Dose Level -2, other dose levels may be considered and implemented after discussions among the Investigators and Sponsor's Medical Monitor.

It is anticipated that at least 3 patients will be treated at each dose level per treatment arm. If no patients experience a DLT, then the subsequent 3 patients will be treated at the next planned dose level.

If DLT is observed in ≥ 2 of 3 patients in either treatment DRs at any dose level, no further dose escalation will occur in that DR, and the current dose will be defined as the maximum administered dose (MAD).

If DLT is observed in 1 of 3 patients in a cohort at any dose level, then up to 6 patients total will be enrolled at that same DR at that dose level. If DLT is observed in ≥ 2 patients in the expanded cohort, then no further dose escalation will occur, and the current dose will be defined as the MAD, unless the SRC decides that there is sufficient clinical uncertainty about the DLTs that warrants the enrollment of up to 6 additional patients. In the event of additionally enrolled patients, if a DLT is observed in 33% or more DLT-evaluable patients in the entire cohort, then no further dose escalation will occur, and the current dose will be defined as the MAD for the dosing regimen under consideration. After the MAD is defined, either the previously administered lower dose will be expanded to a total of 6 patients, or an intermediate (between the MAD and the next lower dose level) will be investigated in up to 6 patients. The highest dose tolerated without DLT in at least 5 of 6 patients (i.e. <33% of DLT-evaluable patients experiencing a DLT) in a cohort from one treatment arm will be defined as the MTD for that treatment arm. Additional patients may be added to further explore the MTD or OBD prior to expansion.

Based on review of available safety and PK data during this and other studies with ALRN-6924, dose escalation or modification steps may be adjusted (i.e. increased or decreased) by the SRC to limit the number of patients exposed to sub-therapeutic dose levels as well as to ensure patients' safety. Additional patients may be added to further explore safety at a dose level or to confirm a certain dose as an MTD or OBD.

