- If a DLT is observed in 1 of 3 patients in a cohort at any dose level, then up to 6 patients total will be enrolled in the same DR at that dose level. If a DLT is observed in 2 or more patients in the expanded cohort, then no further dose escalation will occur, and the current dose will be defined as the MAD, unless the SRC decides that there is sufficient clinical uncertainty about the DLTs that warrants the enrollment of up to 6 additional patients. In the event of additionally enrolled patients, if a DLT is observed in 33% or more DLT-evaluable patients in the entire cohort, then no further dose escalation will occur, and the current dose will be defined as the MAD for the dosing regimen under consideration.
- After the MAD is defined, either the previously administered lower dose will be expanded to a total of 6 patients, or an intermediate dose (between the MAD and the previous dose level) will be investigated in a total of 6 patients. The highest dose tolerated in at least 5 of 6 patients (i.e. $<33\%$ of DLT-evaluable patients experiencing a DLT) will be defined as the MTD or OBD. Additional patients may be added to further explore the MTD or OBD prior to expansion.

The SRC may hold the dose (e.g., stop dose escalation) at their discretion and enroll additional patients until sufficient safety data are obtained to determine escalation of the current dose level or to confirm a certain dose level as an MTD or OBD.

Dose Level and Dose Regimen – Phase 2a dose expansions

Based on the safety, efficacy and PK/PD profile of ALRN-6924 from the dose escalation portion of the study as well as data from other clinical trials and preclinical data, three dosing regimens of ALRN-6924 administered as single agent therapy (DR-A, DR-B, DR-C) will be tested in Phase 2a EXP in PTCL to determine the optimal dosing regimen.

For patients with MDM2 amplified or MDM2/CDK4 co-amplified solid tumors, patients will receive ALRN-6924 in combination with palbociclib. Palbociclib will be administered at an oral dose of 100 mg daily (Days 1-21) in combination with ALRN-6924, which will be administered at 3.1 mg/kg on Days 1, 8, and 15 of a 28-day cycle (or as otherwise determined during the safety run-in period for this cohort).

The decision to begin palbociclib below the approved dose level of 125 mg is based on the frequency of required

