5.9.3 Definition of Maximum Tolerated Dose

The MTD is defined as the dose at which ≤ 1 of 6 patients experiences a treatment-related toxicity that qualifies as a DLT, with the next higher dose having ≥ 2 of up to 6 patients experiencing a DLT.

The MTD will not be established until all patients enrolled in the cohort have completed Cycle 1, discontinued treatment or had a dose reduction. Previously established tolerability of a dose level will be reevaluated if toxicities that would have been DLTs in Cycle 1 are observed in later cycles.

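### After the two-DLT stop is met, the number of added patients is left open, so one DLT-free patient (2 of 7) lifts the mandatory stop

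*Protocol*

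**What the plan says.** Protocol 5.7.1 sets the 3+3 path: "If DLT is observed in 1 of 3 patients in a cohort at any dose level, then up to 6 patients total will be enrolled". If a DLT is then observed in two or more "patients in the expanded cohort, then no further dose escalation will occur, and the current dose will be defined as the MAD". The MAD is the maximum administered dose. An exception follows at once: the stop holds "unless the SRC decides that there is sufficient clinical uncertainty about the DLTs that warrants the enrollment of up to 6 additional patients". If patients are added, "if a DLT is observed in 33% or more DLT-evaluable patients in the entire cohort, then no further dose escalation will occur". The synopsis repeats the rule: "In the event of additionally enrolled patients, if a DLT is observed in 33% or more DLT-evaluable patients in the entire cohort", escalation ends. The exception is attached to the expanded cohort only, not to the stop at two or more DLTs in the first three patients.

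Four other places bear on the same decision:

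- 5.6 lets escalation proceed when no more than 33% of patients have a DLT, after Cycle 1 is complete, the SRC has reviewed the cohort and the Medical Monitor has documented the decision. It also lets the SRC hold the dose and "enroll additional patients until sufficient safety data are obtained to determine escalation of the current dose level".
- 5.7.1 describes the MTD as follows: "The highest dose tolerated without DLT in at least 5 of 6 patients (i.e. <33% of DLT-evaluable patients experiencing a DLT").
- 5.9.3 defines the MTD as at most 1 of 6 with a DLT, the next higher dose having two or more "of up to 6 patients experiencing a DLT".
- 8.10.1, and the synopsis text on escalation, make escalation conditional on there being no DLT, with no percentage.

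The SAP covers Phase 1 but adds no decision rule; its section 8.2 only tabulates DLTs.

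**The concern.** The decision rests on two numbers, the DLT count and the number of evaluable patients. The exception opens only when at least two DLTs have occurred, so the SRC picks the second number knowing the first. The protocol caps the addition at six but sets no minimum, does not require the number to be fixed before enrolment, does not limit how often the pooled rate is read, and does not define the uncertainty that opens the extension. A boundary that can be re-read with a growing denominator is easier to cross than one read once.

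At stake is whether a stop that has been met remains a stop, and whether later patients are treated at or above a dose that the 3+3 rule had just closed.

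**Working it through.** **Inputs.** From 5.7.1: expansion after 1 DLT in 3; stop at two or more DLTs in the expanded cohort (taken here as filled to 6); 1 to 6 patients added; stop if the pooled rate is 33% or more. The true DLT rate p is not in the documents; I assume 20%, 33% and 40%. Write q = 1 − p. Patients are taken as independent and the SRC as always using the extension.

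**Step 1: the plan's own equivalence.** 5.7.1 equates at least 5 of 6 without a DLT with a rate below 33%. 1/6 = 16.7% is below and 2/6 = 33.3% is not, so it reproduces at n = 6.

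**Step 2: the boundary beyond six.**

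- 2/7 = 28.6%, 2/8 = 25.0%, 2/9 = 22.2%: all below 33%.
- 3/9 = 33.3% is a stop; 3/10 = 30.0% is not.
- 4/12 = 33.3% is a stop.

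The most DLTs that clear the dose are 2 at n = 7 to 9 and 3 at n = 10 to 12. After 2/6 one DLT-free patient is enough; after 3/6, four in a row. This step needs no assumption about p.

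**Step 3: chance that 2/6 is cleared, single read.** For 1, 2 or 3 added patients no further DLT is allowed: q, q², q³. For k = 4, 5 or 6 added, at most one is allowed: q^k + k·p·q^(k−1).

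| Patients added | p = 33% | p = 40% |
|---|---|---|
| 1 | 67% | 60% |
| 2 | 45% | 36% |
| 3 | 30% | 22% |
| 4 | 60% | 48% |
| 5 | 47% | 34% |
| 6 | 36% | 23% |

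**Step 4: a look after each added patient, up to six.** From 2/6 the dose clears at n = 7 if the first added patient has no DLT. Otherwise the count is 3/7, and three DLT-free patients in a row are needed to reach 3/10. A fourth DLT cannot be cleared by n = 12. So P = q + p·q³.

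- p = 33%: 0.67 + 0.33 × 0.301 = 0.769
- p = 40%: 0.60 + 0.40 × 0.216 = 0.686
- p = 20%: 0.80 + 0.20 × 0.512 = 0.902

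From 3/6 the chance is q⁴: 20% at p = 33% and 13% at p = 40%.

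**Step 5: whole path at one dose level.** Without the extension, P = q³ + 3pq²·q³. The extension adds P(2/6) and P(3/6), each times its chance of clearing, where P(2/6) = (3pq²)² and P(3/6) = 3pq²·3p²q. At p = 33%: 0.434 + 0.198 × 0.769 + 0.097 × 0.202 = 0.606.

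| True DLT rate | No extension | Look after each, up to 6 | Exactly 6, one read |
|---|---|---|---|
| 20% | 70.9% | 85.7% | 81.5% |
| 33% | 43.4% | 60.6% | 51.4% |
| 40% | 30.9% | 45.4% | 35.9% |

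**Step 6: the status of a cleared 2/7.** It satisfies the below-33% wording of the MTD sentence in 5.7.1 and the synopsis. It does not satisfy the 5-of-6 wording in the same sentence, nor the limit of 1 of 6 in 5.9.3. The limits in 5.6 (more than 33%) and 5.7.1 (33% or more) agree at 2/6 if 33% means 33.0%, since 33.3 exceeds it. If it means one third, 2/6 is a stop under 5.7.1 but not under 5.6.

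**The case against.** A reader might infer four stronger things, and the documents support none of them.

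- **That a stop becomes an automatic go.** Falling below 33% only removes the compulsory stop. The SRC must first find clinical uncertainty about the DLTs. Sections 5.6 and 8.10.1 then require Cycle 1 to be complete, the SRC to review the cohort and confirm the next dose, and a written decision.
- **That the re-read clears a dose at the 33% limit more often than not.** With a single read this holds only when 1 or 4 patients are added. The 77% figure needs a formal review after every added patient, which no section describes, although none rules it out.
- **That the rule can no longer tell acceptable from unacceptable doses.** Over the whole path, the gap between true rates of 20% and 40% is 70.9 − 30.9 = 40.0 points without the extension and 85.7 − 45.4 = 40.3 with looks after each patient. The rule shifts towards escalation without losing this contrast.
- **That 2 of 7 makes a dose the MTD.** It meets one wording and fails two. Section 5.9.3 also withholds the MTD until every patient in the cohort has finished Cycle 1, stopped treatment or been dose-reduced.

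The sentence in 5.6 on enrolling until data suffice is first of all a power to hold the dose. The practical reach is also limited. DR-A and DR-A-2 are closed after two DLTs each, with no extension recorded, and an expansion dose for DR-B is already listed. Assuming that the SRC always uses the extension gives an upper bound.

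All of that stands. It does not remove the point: the same committee opens the extension and chooses its size, so its discretion cannot supply the missing limit on that choice.

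**Conclusion.** The point holds as a defect in a stated rule, of moderate weight. Once the two-DLT stop has been met, whether it stays met depends on a sample size chosen after the DLTs are known. That one DLT-free patient lifts the mandatory stop follows from the protocol's own figures.

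The size rests on assumed DLT rates, independent patients and use of the extension. From 2/6 at a true rate of 33%, a single read clears the dose with probability 30% to 67% depending only on how many are added; at 40% the range is 22% to 60%. Looks after each patient raise these to 77% and 69%. Across the whole path, looks after each patient raise the chance of being allowed to escalate at a true 33% from 43% to 61%.

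The point applies to any dose level still open, such as in DR-B, and to how a cohort with two or more DLTs is classified when the MTD is reported.

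**What to change.** In 5.7.1 and the synopsis, require the SRC to record, before enrolling any added patient, how many DLT-evaluable patients will be added. The pooled rate should be read for clearing the dose once, when all of them have completed Cycle 1; earlier review may only stop. Make the sentence in 5.6 on enrolling until data suffice subject to this.

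Reconcile the extension's limit of 33% or more with the limit of more than 33% (5.6 and the start of 5.7.1), the 5-of-6 wording (5.7.1 and synopsis), the 1-of-6 and 2-of-up-to-6 wording (5.9.3) and the no-DLT condition (8.10.1 and synopsis), so that a cohort with two or more DLTs has one status. Which threshold applies, and what minimum number, is for the sponsor. Without a minimum, the SRC could still commit to one patient, so this part of the decision matters.

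The change is one of wording. The cost is a somewhat slower decision when the extension is used, and a less permissive rule at low toxicity too. For illustration only, with six added and one read, a 2/6 cohort at an assumed true rate of 20% is cleared with probability 66% instead of 90%, and the whole-path chance moves from 85.7% to 81.5%.

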5.7.2 Dose Levels for the Expansion Portion of the Study

The EXP will enroll up to 5 distinct groups of patients with specific solid tumors and/or lymphomas to further investigate the clinical safety profile and potential efficacy of ALRN 6924 at the MTD, OBD, or an alternative dosing regimen. PTCL has been selected as one of the EXP groups to be further studied; up to 3 cohorts in PTCL may be studied in order to determine the optimal dosing regimen. Another Phase 2a EXP group will include patients with MDM2 amplified or MDM2/CDK4 co-amplified solid tumors who will receive ALRN-6924 in combination with palbociclib.

Phase 2a Expansion in PTCL

Two DLTs were observed at DL-7A (hypotension and hepatobiliary laboratory abnormalities) rendering DL-7A the maximum administered dose whereas in DL-6A, only one DLT was observed (fatigue) in six DLT-evaluable patients. Furthermore, a complete remission has been observed in a PTCL patient at DL-5A (2.1 mg/kg). Therefore, the first selected dose and schedule for the Phase 2a expansion in PTCL is

3.1 mg/kg on Days 1, 8, and 15 of a 28 day cycle (DL-6A). Alternative dosing regimens to be tested may include 2.7 mg/kg on Days 1, 4, 8, and 11 of a 21 day cycle (DR-B) and 3.1 mg/kg on Days 1, 3, and 5 of a 21 day cycle (DR-C). Six to 8 patients will be enrolled in DR-C in a run-in part and the treating investigators, along with the Medical Monitor, will review safety and tolerability through Cycle 1 prior to opening the full DR-C expansion cohort. Lower dose levels for DR-C, in 25% reductions in the starting dose, may be assessed if the safety and tolerability of 3.1 mg/kg are not acceptable. Should this occur, 6-8 patients will again be enrolled into a run-in part and the treating investigators and Medical Monitor will meet again to review all patients prior to opening the full DR-C expansion cohort. For each dose level assessed during the run-in part, the SRC will use the DLTs defined in Phase 1 as a guide for determining safety.

Phase 2a Expansion in MDM2 amplified or MDM2/CDK4 co-amplified solid tumors

ALRN-6924 and palbociclib have not previously been co-administered in humans. Therefore, for the Phase 2a cohort of patients with MDM2 amplified or MDM2/CDK4 co-amplified solid tumors, a safety run-in group of 6-8 patients will first be enrolled and evaluated by the sponsor and the primary investigators before further patients are permitted to enroll. The SRC will use the DLTs defined in Phase 1 and the toxicity profile of palbociclib (in accordance with the package insert) as a guide for assessing safety.

Enrollment of the first 3 patients in this cohort will be separated in time by at least one week each, to assess for unexpected acute toxicities related to administration of the treatment regimen. Patients will receive ALRN-6924 at the previously determined recommended Phase 2 dose for the once-weekly administration schedule (3.1 mg/kg on Days 1, 8, and 15) and palbociclib at an oral dose of 100 mg daily for 21 days (one dose level below the approved oral dose of 125 mg) in a 28-day cycle. In the event that this regimen is not determined to be safe or tolerable at these dose levels, the dose of ALRN-6924 will be decreased by 25% and/or the dose of palbociclib will be decreased by one dose level (to 75 mg/day), as needed based on the pattern of toxicities encountered, and an additional 6-8 patients will be assessed in a safety run-in using the reduced dose level, before further enrollment is permitted. Subsequent reductions of the ALRN-6924 dose by 25% may be implemented if safety and tolerability are still not acceptable. The decision to begin palbociclib below the approved dose level is based on the frequency of required dose reductions, often due to neutropenia. The SRC may consider adjusting to the approved palbociclib dose, if palbociclib-related toxicities are not prohibitive and patient benefit is expected to outweigh risk. Once the safety run-in is complete, all subsequent patients will be enrolled at the recommended dose level.

